### 11.1 Primary Efficacy Analysis

The primary efficacy endpoint of ORR is defined as a best response of CR or PR as determined by the investigator. Response and/or progression are evaluated using the RECIST 1.1 criteria. The ORR will be summarized with frequencies and percentages.

The confirmed response rate will be calculated for patients with sufficient data to determine if the patient has a confirmed response or has progressive disease, otherwise patients will be classified as inevaluable for confirmed response at the time of analysis.

As a secondary endpoint, ORR will be evaluated per the IRR.

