### **9.8.2 Efficacy Evaluations**

#### 9.8.2.1 Tumor Assessments

Tumor assessments will be performed at screening; at the end of Cycles 2, 4, and 6 (between Days 14 and 21); every 3 cycles after Cycle 6 (between Days 14 and 21); and at the End of Treatment visit. Tumor response will be interpreted using RECIST Version 1.1 ([Appendix A](#)).

If an initial CR or PR is noted at Cycle 7 or beyond, confirmatory scans must be performed 4 to 6 weeks later. In the case of SD, follow-up measurements must have met the SD criteria at least once after study entry at a minimum interval of no less than 6 to 8 weeks.

Patients who continue treatment with CO-1686 post-progression should continue to be scanned according to the protocol until they discontinue from the study.

Tumor assessments should consist of clinical examination and appropriate imaging techniques (preferably CT scans of the chest, abdomen, and pelvis with appropriate slice thickness per RECIST Version 1.1); other studies (MRI and X-ray) may be performed if required. The same methods used to detect lesions at baseline are to be used to follow the same lesions throughout the clinical study.

Brain imaging (MRI/CT) is required at baseline. Patients with known brain metastases and/or brain lesions detected at baseline are required to repeat brain imaging as part of the follow-up tumor assessments. The same methods used to detect brain lesions at baseline are to be used to follow the same lesions throughout the clinical study.

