##### **Objective Response Rate (ORR) - Primary Endpoint**

A primary endpoint in Phase 2 of the study (objective response rate) is the best response recorded from the start of the treatment until disease progression or recurrence. The frequency and percentages of patients with a best response of CR, PR, stable disease (SD), or progressive disease (PD) will be summarized for the tumor-evaluable and safety populations enrolled in Phase 2. The response rate (CR+PR) will also be presented with frequencies and percentages.

For patients who continue treatment post-progression, the first date of progression will be used for the analysis.

The ORR will be evaluated by the investigator with the primary analysis based on investigator assessment.

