## Evaluation of Best Overall Response

The best overall response is the best response recorded from the start of the treatment until disease progression/recurrence (taking as reference for PD the smallest measurements recorded since the treatment started). The patient's best response assignment will depend on the achievement of both measurement and confirmation criteria.

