### Time Point Response

A response assessment will occur at the protocol-specified time points. The tables below provide a summary of the overall response status calculation at each time point for patients who have measureable and non-measureable disease (non-target disease only).

Time Point Response: Patients with Target (+/- non-target) Disease			
Target Lesions	Nontarget Lesions	New Lesions	Overall Response
CR	CR	No	CR
CR	Non-CR/non-PD	No	PR
CR	Not evaluated	No	PR
PR	Non-PD or not evaluated	No	PR
SD	Non-PD or not evaluated	No	SD
Not Evaluated	Non-PD	No	NE
PD	Any	Yes or No	PD
Any	PD	Yes or No	PD
Any	Any	Yes	PD

NE=Not evaluable.

Evaluation of Best Overall Response When Confirmation of CR and PR Required		
Overall Response First Time Point	Overall Response Subsequent Time Point	Best Overall Response
CR	CR	CR
CR	PR	SD, PD or PR a
CR	SD	SD provided minimum criteria for SD duration met, otherwise, PD
CR	PD	SD provided minimum criteria for SD duration met, otherwise, PD
CR	NE	SD provided minimum criteria for SD duration met, otherwise, NE
PR	CR	PR
PR	PR	PR
PR	SD	SD
PR	PD	SD provided minimum criteria for SD duration met, otherwise, PD
PR	NE	SD provided minimum criteria for SD duration met, otherwise, NE
NE	NE	NE

a If a CR is truly met at first time point, then any disease seen at a subsequent time point, even disease meeting PR criteria relative to baseline, makes this disease PD at that point (since disease must have reappeared after CR). Best response would depend on whether minimum duration for SD was met. However sometimes 'CR' may be claimed when subsequent scans suggest small lesions were likely still present and in fact the patient had PR, not CR at the first time point. Under these circumstances, the original CR should be changed to PR and the best response is PR.

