### **Confirmatory Measurement/Duration of Response**

#### Confirmation

CT scans are required within 7 days prior to the start of Cycles 3, 5, and 7, and then within 7 days prior to the start of every third cycle of treatment thereafter, beginning with Cycle 10. If an initial CR or PR is noted at Cycle 7 or beyond, confirmatory scans must be performed 4 to 6 weeks later. In the case of SD, follow-up measurements must have met the SD criteria at least once after study entry at a minimum interval of no less than 6 to 8 weeks.

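### SAP 11.1 most naturally makes the primary ORR unconfirmed, in conflict with protocol Appendix A, and its confirmed-rate rule lets outcome and follow-up set the denominator

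*SAP*

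**What the plan says.** SAP 11.1 defines the endpoint in one sentence: "The primary efficacy endpoint of ORR is defined as a best response of CR or PR as determined by the investigator". It names RECIST 1.1 as the criteria and does not say whether a response must be confirmed. The next paragraph introduces a separate confirmed response rate. Its denominator is limited to "patients with sufficient data to determine if the patient has a confirmed response or has progressive disease". Everyone else falls outside that denominator, under the closing clause of the same sentence: "otherwise patients will be classified as inevaluable for confirmed response at the time of analysis". ORR by independent radiology review (IRR) follows as a secondary endpoint, also without a confirmation rule.

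Protocol 11.2.4.2 is silent too: the ORR "is the best response recorded from the start of the treatment until disease progression or recurrence".

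Protocol 9.8.2.1 says "Tumor response will be interpreted using RECIST Version 1.1" and points to Appendix A. There, the patient's "best response assignment will depend on the achievement of both measurement and confirmation criteria". The table headed "Evaluation of Best Overall Response When Confirmation of CR and PR Required" turns a PR followed by SD into SD, and a PR followed by PD or a non-evaluable scan into SD, PD or not evaluable, but never PR. Appendix A also provides a dedicated scan for late responses: "If an initial CR or PR is noted at Cycle 7 or beyond, confirmatory scans must be performed 4 to 6 weeks later".

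SAP Section 15 lists six changes from the protocol analyses. None is a change to the confirmation requirement. Item 2 says only that the handling of ongoing patients for ORR was clarified, without saying how.

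**The concern.** There are two linked faults.

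First, the SAP and Appendix A point to different primary endpoints. An analyst working from SAP 11.1 would probably count every investigator CR or PR. An analyst who follows the RECIST reference into Appendix A would count only confirmed ones. Both could defend their figure, and ORR is a primary efficacy variable (SAP 10.1). Duration of response is also primary there, and SAP 11.2.1 restricts it to patients with a CR or PR, so its responder set is open in the same way.

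Second, the confirmed rate does not settle the matter, because its denominator is not fixed in advance. Whether a patient is counted depends on what happened to that patient and on how long follow-up ran. This SAP serves the NDA and MAA submissions while the study is ongoing, so some responses can be expected to be pending at cutoff.

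**Working it through.** **Inputs.** Protocol 3.4.1.1 and Table 5, centrally T790M-positive Phase 1 patients, cutoff 6 March 2014. There are 22 patients with a recorded best response: 14 PR, 6 SD, 2 PD. Nine responses had had the chance to be confirmed and 7 were. So 9 − 7 = 2 were checked and not confirmed, and 14 − 9 = 5 were pending. Two further patients had not reached their first scan and are outside the 22.

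**Reproducing the plan's figures.** 14/22 = 63.6% (stated as about 64%) and 7/9 = 77.8% (stated as 78%). Both agree. One cell of Table 5 does not: 7 responders among 9 evaluable patients at 900 mg BID free base is shown as 87.5%, but 7/9 = 77.8%. The overall row is unaffected.

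**The same 22 patients under each rule** (exact 95% CI where given):

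- Unconfirmed ORR: 14/22 = 63.6% (40.7 to 82.8).
- Confirmed, all 22 kept, pending counted as not confirmed: 7/22 = 31.8% (13.9 to 54.9).
- Confirmed, all 22 kept, all five pending later confirm: (7 + 5)/22 = 12/22 = 54.5% (32.2 to 75.6).
- SAP rule, with *determine if* read as *determine whether*, so that only the five pending drop out: 7/(7 + 2 + 6 + 2) = 7/17 = 41.2% (18.4 to 67.1).
- SAP rule read literally, so that only patients with a confirmed response or PD count. With *k* of the 6 SD patients having progressed, the rate is 7/(9 + k) if the two unconfirmed responders have not progressed, and 7/(11 + k) if both have. At k = 0 this is 7/9 = 77.8% or 7/11 = 63.6%. At k = 6 it is 7/15 = 46.7% or 7/17 = 41.2%. The documents do not give the later status of these patients.

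**Direction.** 7/17 is 9.4 points above the 31.8% floor (41.2 − 31.8) and 13.3 points below the 54.5% ceiling (12/22 − 7/17). Applying the observed 7/9 to the five pending gives (7 + 3.9)/22 = 49.5%, which is also above 41.2%. So dropping only the pending responders can err either way relative to the eventual rate. The literal reading is different: 63.6% and 77.8% both exceed the 54.5% that would result if every response already recorded were confirmed.

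**Who drops out.** Pending responders, and patients who stop without enough data, leave the denominator on any reading. Ongoing SD leaves only on the literal reading.

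**Filing cutoff.** SAP 2.4 covers 500 and 625 mg BID patients enrolled by 31 December 2014, with data to 29 April 2015. Assume Day 1 on the enrolment date and scans on schedule. The scan windows close on study days 42, 84, 126 and 189 (end of Cycles 2, 4, 6 and 9).

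- First response at Cycle 2: checked at Cycle 4, by 24 March 2015 for a 31 December start. All such patients can be checked.
- First response at Cycle 4: checked at Cycle 6, which closes by cutoff for starts up to 25 December 2014.
- First response at Cycle 6: the next scheduled scan is at Cycle 9, which closes by cutoff for starts up to 23 October 2014. Appendix A, however, names scans by the cycle they precede. If the end-of-Cycle-6 scan counts as a Cycle 7 finding, the 4-to-6-week scan applies, confirmation is due by day 126 + 42 = 168, and the date moves to 13 November 2014.

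**The case against.** The strongest reply is that SAP 11.1 is not really ambiguous. It gives an ORR and then, separately, a confirmed rate. Protocol 11.2.4.2 omits confirmation, and Protocol 3.4.1.1 uses ORR for 14/22 while noting that some responses are too recent to confirm. The Appendix A table is headed conditionally. This stands as far as it goes: unconfirmed is the most natural reading, and both rates are planned, so the confirmed result is not hidden. It does not remove the conflict. The Appendix A sentence on best response carries no such condition, and Section 15 records no departure from it.

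It is also fair to say that no alpha, target rate or power is stated for ORR. The summary is descriptive, so no formal test turns on the choice.

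Three stronger inferences are tempting, and the documents do not support them.

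- *The confirmed-rate rule always inflates.* That holds only against the 7/22 floor. Dropping pending responders alone gives a figure between the floor and the ceiling.
- *The inflation is about 46 points* (77.8 − 31.8). This needs the literal reading, no SD patient progressed, neither unconfirmed responder progressed, and the floor as comparator.
- *The primary ORR must be confirmed, or Section 15 item 2 makes the inevaluable rule govern it.* Which version is primary is the sponsor's choice, and SAP 11.1 writes the rule only for the confirmed rate.

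**Conclusion.** The point holds in two parts. The SAP's most natural primary ORR is unconfirmed, in undeclared conflict with Appendix A. The separate confirmed rate has a denominator set by outcome and length of follow-up.

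In the Phase 1 snapshot, requiring confirmation moves the rate from 63.6% to between 31.8% and 54.5%. The confirmed-rate rule gives 41.2% on the milder reading and 41.2% to 77.8% on the literal one. These figures come from 22 patients at mixed doses with immature data, and assume that the recorded best responses of the SD and PD patients, and the two failures to confirm, do not change. They show how far the definitions can part; they do not forecast the filing analysis.

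The filing effect cannot be computed from the documents. It should be smaller, because Cycle 2 responses, and nearly all Cycle 4 responses, can be checked by cutoff. The pending cases would be mainly late first responses.

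**What to change.** 1. In SAP 11.1, state whether the primary investigator ORR is confirmed or unconfirmed. Reconcile that with protocol 11.2.4.2 and Appendix A, and list any departure in Section 15. Either choice is workable if declared.
2. Delete the inevaluable rule. Compute the confirmed rate over the full stated analysis population, counting SD, unconfirmed, pending and not-evaluable patients as not confirmed. Report the number pending at cutoff and, optionally, the upper bound if all of them confirm.
3. Use the same stated definition for ORR by IRR and for the responder set in duration of response.

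The change is wording only and needs no new scans. The price is a somewhat lower stated confirmed rate wherever the present rule would drop patients, with late first responses counted as not confirmed at cutoff. The pending count makes that visible.

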### 4 ANALYSIS POPULATIONS

**PK-Evaluable Population**—all patients who have received at least one dose of CO-1686 and have had adequate PK assessments drawn for determination of the PK profile. Adequacy will be determined on a case-by-case basis and will be assessed prior to analysis of the blood samples.

**Food-Effect PK Population**—all patients participating in the food-effect PK evaluation in Phase 1 of the study who received CO-1686 on both Day -7 and Day 1 (Cycle 1) complied with the fed and fasted requirements, and have sufficient PK data for a comparison to be made between the fasted and fed state.

**ECG/PK Comparison-Evaluable Population**—all patients in Phase 1 and Phase 2 who have received CO-1686 and have had adequate PK and ECG assessments performed for determination of the ECG effects and the relationship between PK and ECG

**Safety Population**—all patients who have received at least one dose of CO-1686.

**DLT-Evaluable Population**—all patients enrolled into Phase 1 of the study who received at least 80% of Cycle 1 scheduled doses of CO-1686 and completed Cycle 1 or who experienced a DLT in Cycle 1.

**Tumor-Evaluable Population**—all patients who received at least one dose of CO-1686, have measurable tumor lesions at baseline, and have at least one postbaseline disease assessment. Patients that died prior to receiving at least one postbaseline disease assessment will also be included.

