## 11 EFFICACY ANALYSIS

All efficacy evaluations will be conducted in patients that are centrally confirmed to be T790M positive using the efficacy-evaluable and safety populations, unless otherwise specified.

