### 15 SUMMARY OF CHANGES FROM PROTOCOL SPECIFIED ANALYSES

Due to the conditional/accelerated approval strategy, the initial MAA and NDA submission data sets will focus on the subset of patients treated at 625mg BID or 500mg BID and enrolled up to the 31st of December with data as of April 2015.

The following changes from the protocol specified analyses are contained in this SAP:

1. The patients with death before first post-baseline scan will be included in the ORR analysis with the category of 'Death before first post-baseline scan'. This means that the tumor evaluable population was changed to an efficacy analysis population including those with death before first scan
2. Clarified how ongoing patients are analyzed for ORR
3. Added the duration of treatment in patients with a CR or PR
4. PFS analyses are not included since the study is still ongoing
5. PRO analyses are not included since the study is still ongoing
6. Analyses of the time to adverse events that results in a dose reduction, interruption, or discontinuation of study drug are included.

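### Read literally, SAP 11.1 bases the confirmed response rate only on patients with a confirmed response or PD, so the denominator depends on outcome and can only raise the rate

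*SAP*

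**What the plan says.** SAP 11.1 first defines primary ORR as CR or PR by investigator assessment, with no mention of confirmation. It then adds a second rate: "The confirmed response rate will be calculated for patients with sufficient data to determine if the patient has a confirmed response or has progressive disease". For all remaining patients the same sentence gives this rule: "otherwise patients will be classified as inevaluable for confirmed response at the time of analysis".

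The surrounding text bears on how that sentence should work:

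- SAP Section 11 runs efficacy evaluations in centrally confirmed T790M-positive patients, "using the efficacy-evaluable and safety populations, unless otherwise specified".
- SAP Section 4, on the tumor-evaluable population: "Patients that died prior to receiving at least one postbaseline disease assessment will also be included".
- SAP Section 15, item 1: "The patients with death before first post-baseline scan will be included in the ORR analysis", with a category of their own. Item 2 reads in full: "Clarified how ongoing patients are analyzed for ORR".
- Protocol 11.2.4.2 says that the counts of CR, PR, SD and PD "will be summarized for the tumor-evaluable and safety populations enrolled in Phase 2".
- Protocol Appendix A, in the table headed "Evaluation of Best Overall Response When Confirmation of CR and PR Required", assigns a PR followed by SD a best response of SD. Its text on best overall response makes the assignment depend on confirmation as well as measurement.
- SAP 2.4 sets the data cutoff at 29 April 2015 for patients at 500 or 625 mg BID enrolled by 31 December 2014. Patients at other doses enrolled by that date are cut at 31 December 2014.

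**The concern.** The sentence in 11.1 names two outcomes that make a patient evaluable: a confirmed response and progression. A patient with neither has no stated place in the denominator. That group includes patients with stable disease, patients whose PR was followed by SD, patients who stop without documented PD, and deaths before the first scan. Most of these are settled non-responses, not missing information.

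If the rule is programmed as worded, the rate depends on how many non-responders have already progressed by the cutoff as well as on how many patients responded. A non-responder who stays stable for longer is removed from the denominator and so raises the rate. SAP Section 1 says these analyses will be presented in the NDA and MAA, where a reader would take a confirmed response rate to be a proportion of the stated population.

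**Working it through.** **Notation.** A = confirmed responders; B = patients with PD and no confirmed response; C = all others; N = A + B + C.

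**Exact relation.** Literal rule: A/(A + B). Fixed denominator at the same cutoff: A/N. Their ratio is N/(A + B) = 1/(1 − C/N), which is never below 1. For a fixed-denominator rate of 50%:

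- C/N = 10%: 0.50/0.90 = 55.6%
- C/N = 20%: 0.50/0.80 = 62.5%

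**The protocol's own counts (Protocol 3.4.1.1 and Table 5).** The stated figures reproduce: 14 PR of 22 patients with a non-missing best response = 63.6%; 7 of the 9 responses with an opportunity for confirmation = 77.8%. So 9 − 7 = 2 responses were not confirmed and 14 − 9 = 5 were pending. The other 8 of the 22 were 6 SD and 2 PD. Hold A at 7 and vary only whether the 6 SD and 2 unconfirmed patients have progressed:

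| Denominator | Calculation | Rate |
|---|---|---|
| Literal, none of the 8 progressed | 7/(7 + 2) | 77.8% |
| Literal, the 2 unconfirmed progressed | 7/(7 + 4) | 63.6% |
| Literal, all 8 progressed | 7/(7 + 10) | 41.2% |
| Only the 5 pending set aside | 7/(22 − 5) | 41.2% |
| Fixed | 7/22 | 31.8% |

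The 77.8% in the first row matches the 7/9 confirmation share only by coincidence: here the 9 is 7 confirmed plus 2 PD. With the same seven confirmed responses, the literal rule gives anything from 41% to 78%.

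**How many responses can be truly pending at 500/625 mg BID?** With 21-day cycles and scans on Days 14 to 21, the windows are study days 35–42 (Cycle 2), 77–84 (Cycle 4), 119–126 (Cycle 6) and 182–189 (Cycle 9). Assume first dose at enrolment and scans on schedule. A first dose on 31 December 2014 makes 29 April 2015 study day 120, so even the last patient has passed the Cycle 2 and Cycle 4 windows. A PR first seen at Cycle 2 has therefore been rescanned. A PR first seen at Cycle 4 can be pending only for first doses on 26–31 December, because the Cycle 6 window has closed for 25 December and earlier. A PR first seen at Cycle 6 can be pending for first doses from 24 October if confirmation waits for Cycle 9. Appendix A asks for a scan 4 to 6 weeks after a response first noted at Cycle 7 or beyond, and dates the Cycle 6 scan as before Cycle 7, so that last date is uncertain.

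**Illustrative simulation (29 April 2015 cutoff, 162 scenarios).** Only the scan schedule, the dates and the 7/9 confirmation share come from the documents. Assumed: uniform enrolment from 1 May, 1 July or 1 September to 31 December 2014; confirmed rate before drop-out 35, 45 or 55%; first PR at Cycle 2/4/6 in 72/20/8%; PD at first scan 8 or 15%; death before first scan 3%; median time to PD in SD and unconfirmed PR 1.5, 3 or 5 months; exit without PD 0, 1 or 2% per month.

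- C/N: 8.7 to 42.4% (median 22.2%).
- Responses pending: 1.0 to 3.7% of patients.
- Literal rule minus the eventual confirmed rate: 3.0 to 21.5 points (median 10.5), or 3 to 9 points at 1.5 months to PD and 10 to 22 at 5 months.
- Only pending responses set aside, minus the eventual rate: −1.2 to −0.5 points.

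**The case against.** The best defence is that the sentence is a maturity rule. It speaks of sufficient data and of status at the time of analysis, and item 2 of SAP Section 15 has no other evident referent. Protocol 3.4.1.1 uses the same idea when it restricts its confirmation figure to responses that had the opportunity to be confirmed. On that reading PR then SD is itself the determination that 11.1 asks for, and only pending responses leave; the effect is about a point. This reading is plausible. But the sentence sets no follow-up threshold, is not limited to ongoing patients, and gives no place to deaths or exits without PD. A programmer following the words would not implement it.

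Other points stand in part:

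- A reader might infer a contradiction with SAP Section 11. There is none, because that section allows for exceptions and 11.1 is one. The tension with Section 4 and Section 15 item 1 is also softer than it looks: they concern the tumor-evaluable population and the ORR analysis, and 11.1 does not say whether the confirmed rate belongs to that analysis.
- A reader might infer that primary ORR is biased. The restriction is attached to the confirmed rate only. That rate is descriptive, has no test attached, and is not among the variables in SAP 10.1 to 10.3.
- If the table prints the inevaluable count, the fixed-denominator rate can be recovered. The SAP does not require that count.
- The point about few pending responses does not extend to doses cut at 31 December 2014, where a patient enrolled late may have no follow-up scan.

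**Conclusion.** The concern holds in this form: the rule as worded makes the denominator of the confirmed response rate depend on outcome. Compared with a fixed denominator at the same cutoff, the result can only be equal or higher, by exactly 1/(1 − C/N). That needs no assumption beyond the literal reading.

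A reader might infer that the submission's confirmed rate is inflated by about 10 points. The documents do not support that. C at the real cutoff is not given, and the simulated excesses depend on the literal reading and mainly on a time to PD that no document supplies. The simulation also leaves out 500/625 mg patients enrolled before May 2014. Nor is an excess over the eventual confirmed rate certain: PD can be recorded at the first scan while confirmation needs a later one, so very immature data can push the literal rate below it.

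One question remains open. Protocol 11.2.4.2 and SAP 11.1 do not say that primary ORR needs confirmation, while Appendix A makes best response depend on it. If Appendix A governs, primary ORR is already a confirmed rate on the stated populations, and a second, higher one would need explaining. This should be fixed before the tables are programmed.

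**What to change.** In SAP 11.1:

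1. Use as denominator all patients in the populations already named in SAP Section 11: centrally T790M-positive, in the efficacy-evaluable and the safety populations.
2. Count as non-response SD, unconfirmed CR or PR, NE, no post-baseline scan, death before the first scan, and early discontinuation without a confirmed response.
3. Report on a separate line the number of CR/PR whose confirmation scan was not yet due at the cutoff, and count them as non-response in the main figure. Setting them aside while keeping non-responders would again make the denominator depend on outcome.
4. If a maturity restriction is wanted, define it for all patients by enrolment date or minimum follow-up alone.
5. State in 11.1 and in Section 15 whether primary ORR requires confirmation under Appendix A. If it does not, show both rates.

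The cost is SAP wording and table programming. The confirmed rate becomes less favourable, and it reads slightly low while responses are pending: 0.8 to 3.1 points below the eventual rate in the simulated 29 April 2015 scenarios, and more in a cut with very short follow-up. The separate line for pending responses lets the reader see how much of that shortfall could still be made up.
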